The 9OL site visit will review adverse events and the adverse event diary, collect safety blood labs, perform a physical exam and calculate the mPDAI. A stool sample for the stool bank will be collected from the patient. A pouchoscopy will also be performed.

Phone visit 10OL will evaluate for adverse events and review the adverse event diary. At this point 4 weeks after stopping the oral FMT the patient can stop filling out the daily adverse event diary The patient will be reminded to bring the filled out adverse event diary to site visit 11OL. Additionally, mPDAI will be calculated and the concomitant medications will be assessed.

Site visit 110Lwill collect all pages of the adverse event diary, and review the adverse events, which occurred since visit 100L. A physical exam and blood tests will be performed and the mPDAI will be calculated. The concomitant medications will be reviewed. A stool sample for the stool bank will be collected from the patient.

Site visit 12OL will review new adverse events, concomitant medications and the mPDAI score. A stool sample for the stool bank will be collected from the patient.

On the last phone visit 13OL the coordinator will review serious adverse events only, which may have occurred since visit 12OL.

Study patients experiencing a recurrence of symptoms in the open label extension period

If the study patient is experiencing worsening of disease after the second FMT, antibiotic therapy will be re-initiated as a standard of care approach. The patient will nevertheless be followed up according to the same schedule as patients not experiencing a relapse.

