Formal aspects:

Adverse events

Concomitant medication

Calculation of clinical mPDAI (stool frequency, rectal bleeding, fecal urgency/abdominal cramping, fever)

Stool collection: Stool collection

• Visit 9: Phone visit week 24 (168 +/- 10 days after first transplant)

Formal aspects:

Review if serious adverse events occurred in previous 8 weeks

10. FOLLOW UP VISITS OF PATIENTS PARTICIPATING IN OPEN LABEL EXTENSION AFTER WEEK 4

• Visit 6OL: Site visit week 6 (week 0 OL)

This visit should be performed after the patient completed at least 10 days of antibiotics

Examinations

Vital signs: blood pressure (mm Hg), heart rate (min-1), weight (kg)

Physical examination:

- Head (including ENT and eyes)
- Lymphatic system
- Endocrine system
- Lungs and respiratory tract
- Peripheral vascular system
- Cardiovascular system

- Gastrointestinal tract, liver, spleen
- Urogenital system
- Nervous system
- Muscular and skeletal system
- Skin and connective tissue
- Other

each: actual status: Present finding / normal condition / not examined

Formal aspects:

Concomitant medication Calculation of mPDAI score (before pouchoscopy) Dispense oral FMT capsules Dispense omeprazole 20 mg (1 tablet) daily for 14 days during oral FMT Dispense PDAI diary Dispense adverse events diary for OL follow-up phase

Blood sampling and measurement of laboratory parameters (be performed in the 24 hours before FMT)

- Urine pregnancy test

Pouchoscopy: Evaluation of endoscopic PDAI and perform FMT.

• Visit 7OL: Phone visit week 7 (week 1 OL; 7 days (+1 day) after second transplant)

Formal aspects:

Adverse events (review adverse events diary)

Concomitant medication

Calculation of clinical mPDAI (stool frequency, rectal bleeding, fecal urgency/abdominal cramping, fever)

• Visit 8OL: Site visit week 8 (week 2 OL, 15 + 3 days after second transplant)

Formal aspects:

Adverse events (review adverse events diary)

Concomitant medication

Calculation of clinical mPDAI (stool frequency, rectal bleeding, fecal urgency/abdominal cramping, fever)

Reminder stool collection on day 15, 16 or 17 (day 1-3 after end of oral FMT) and bring in stool. Plan for pouchoscopy visit 9OL

• Visit 9OL: Site visit week 10 (week 4 OL, 28 +/- 3 days after second transplant)

Examinations

Vital signs: blood pressure (mm Hg), heart rate (min-1), weight (kg)

Physical examination:

- Head (including ENT and eyes)
- Lymphatic system
- Endocrine system

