- Lungs and respiratory tract
- Peripheral vascular system
- Cardiovascular system

- Gastrointestinal tract, liver, spleen
- Urogenital system
- Nervous system
- Muscular and skeletal system
- Skin and connective tissue
- Other

each: actual status: Present finding / normal condition / not examined

Measurement of laboratory parameters

Hematology Serum chemistry

Stool collection: Bring in.

Formal aspects:

Concomitant medication

Adverse events (review adverse events diary) Calculation of mPDAI score Pouchoscopy: Evaluation of endoscopic PDAI.

• Visit 10OL: Phone visit week 12 (week 6 OL; 42 +/- 3 days after second transplant)

Formal aspects:

Adverse events (review adverse events diary, which needs to be filled out 28 days after the last FMT, which is week 6 OL)

Concomitant medication

Calculation of clinical mPDAI (stool frequency, rectal bleeding, fecal urgency/abdominal cramping, fever)

• Visit 11OL: Site visit week 14 (week 8 OL; 56 +/- 5 days after second transplant)

Examinations

Vital signs: blood pressure (mm Hg), heart rate (min-1), weight (kg)

Physical examination:

- Head (including ENT and eyes)
- Lymphatic system
- Endocrine system
- Lungs and respiratory tract
- Peripheral vascular system
- Cardiovascular system

- Gastrointestinal tract, liver, spleen
- Urogenital system
- Nervous system
- Muscular and skeletal system
- Skin and connective tissue
- Other

each: actual status: Present finding / normal condition / not examined

Measurement of laboratory parameters

Hematology Serum chemistry

Stool collection: Bring in.

Formal aspects:

Concomitant medication

Adverse events

Calculation of mPDAI score Reminder for stool collection week 16

Collect adverse event diary (filled out until week 60L)

• Visit 12OL: Site visit week 22 (week 16 OL; 112 +/- 5 days after second transplant) Formal aspects:

Adverse events

Concomitant medication

Calculation of clinical mPDAI (stool frequency, rectal bleeding, fecal urgency/abdominal cramping, fever)

Stool collection: Stool collection

• Visit 13OL: Phone visits week 30 (week 24OL 168 +/- 10 days after second transplant)

Formal aspects:

Review if serious adverse events occurred in previous 8 weeks

11. POUCHOSCOPY AND LABORATORY PARAMETERS

• Pouchoscopy (Screening, visit 5 or visit 6OL)

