- Response: Symptomatic improvement of active pouchitis (decrease from baseline in mPDAI clinical subscore ≥ 2 points) and no need for antibiotic therapy at week 4.
- Response: Symptomatic improvement of active pouchitis (decrease from baseline in mPDAI clinical subscore ≥ 2 points) and no need for antibiotic therapy at week 8*.
- Response: Symptomatic improvement of active pouchitis (decrease from baseline in mPDAI clinical subscore ≥ 2 points) and no need for antibiotic therapy at week 16*.

*Only patients who do not continue in open label extension

- Exploratory analyses (OL=Open label):
- Endoscopic improvement of active pouchitis (decrease from baseline in mPDAI endoscopic subscore ≥ 2 points) at in open label extension week 8.

- Clinical remission (mPDAI score ≤4 points and a decrease in the baseline mPDAI> 2 points) and no need for antibiotic therapy at week 10 OL.
- Clinical remission (clinical mPDAI score ≤ 4) and no need for antibiotics at week 14 OL.
- Clinical remission (clinical mPDAI score ≤ 4) and no need for antibiotics at week 22 OL.
- Response: Symptomatic improvement of active pouchitis (decrease from baseline in mPDAI clinical subscore ≥ 2 points) and no need for antibiotic therapy at week 10 OL.
- Response: Symptomatic improvement of active pouchitis (decrease from baseline in mPDAI clinical subscore ≥ 2 points) and no need for antibiotic therapy at week 14 OL.
- Response: Symptomatic improvement of active pouchitis (decrease from baseline in mPDAI clinical subscore ≥ 2 points) and no need for antibiotic therapy at week 22 OL.
- Symptomatic worsening of active pouchitis (decrease from baseline in mPDAI clinical subscore ≥ 2 points) from FMT week 0 week 16
- Quantitative changes in mPDAI from baseline values
- Quantitative changes of calprotectin from baseline
- Alterations in stool microbiome after FMT
- Engraftment of donor FMT

Clinical analyses

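### The open-label endoscopic improvement endpoint is set at week 8, when no pouchoscopy is scheduled; it should be tied to the visit 9OL pouchoscopy

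*Combined protocol and SAP*

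**What the plan says.** **Endpoint.** The exploratory lists in Section 1, Section 5 and Section 20 each define open-label endoscopic improvement as a fall of at least 2 points in the endoscopic subscore, timed "at in open label extension week 8". None says whether the week is counted from the first or the second transplant, or which pouchoscopy is the baseline.

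**Open-label visits (Section 10).**
- Visit 6OL, at the second transplant: "Pouchoscopy: Evaluation of endoscopic PDAI and perform FMT".
- Visit 8OL: "Site visit week 8 (week 2 OL, 15 + 3 days after second transplant". No pouchoscopy is listed, and staff are told to arrange one for 9OL.
- Visit 9OL: "Site visit week 10 (week 4 OL, 28 +/- 3 days after second transplant". It includes "Calculation of mPDAI score Pouchoscopy: Evaluation of endoscopic PDAI". Section 7 says the same of this visit: "A pouchoscopy will also be performed".
- Visit 11OL: "Site visit week 14 (week 8 OL; 56 +/- 5 days after second transplant". No pouchoscopy is listed.

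**Section 11.** The heading on timing reads "Pouchoscopy (Screening, visit 5 or visit 6OL" and leaves out 9OL.

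**Missing data.** Under Clinical analyses, Section 20 counts subjects whose endpoint status cannot be determined as non-responders in the intention-to-treat analysis.

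**The concern.** An endoscopic endpoint needs an endoscopy at its time point, and this one has none. Three consequences follow.

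1. The analyst has to choose the visit, and with it the result, after open-label data have been seen.
2. The baseline is open as well. Extension patients have a pouchoscopy at week 0 and another at 6OL, just before the second transplant. A 2-point fall can be met against one and not the other.
3. If the non-responder rule were carried over without thought, the endpoint would be reported as no improvement in anyone.

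Visit 9OL carries most of the endoscopic information on these patients. Under Section 8 the visit 5 pouchoscopy is for patients in clinical remission. Note a to the Section 21 charts adds only those with active disease who decline the extension. Patients who enter the extension will therefore generally have no other scheduled post-treatment endoscopic score, and no endpoint names the visit that supplies it. Section 20 intends the estimates to inform a larger trial, which requires a defined time point and baseline.

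**Working it through.** The plan gives no figure for this endpoint, so the check sets the endpoint against the schedule.

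**Step 1: locate week 8.** Inputs are the Section 10 visit list and the open-label chart in Section 21, which puts the second transplant at day 38 (study week 6).

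| Visit | Days after 2nd transplant (window) | Chart day | Study week | Extension week | Pouchoscopy |
|---|---|---|---|---|---|
| 6OL | 0 | 38 | 6 | 0 | yes, with transplant |
| 8OL | 15 (15 to 18) | 38 + 15 = 53 | 8 | 2 | no |
| 9OL | 28 (25 to 31) | 38 + 28 = 66 | 10 | 4 | yes |
| 11OL | 56 (51 to 61) | 38 + 56 = 94 | 14 | 8 | no |

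The Section 21 chart marks pouchoscopy only at 6OL and 9OL. It flags the mPDAI at 8OL and 11OL as the clinical score only, so no endoscopic subscore is planned at either visit. The three post-transplant windows do not overlap, so a permitted visit window cannot bring the 9OL examination to week 8.

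**Step 2: distance to the usable score.** If week 8 means study week 8, 9OL comes 66 − 53 = 13 days later. If it means extension week 8, 9OL comes 94 − 66 = 28 days earlier. The other timed items in the exploratory list (weeks 10, 14 and 22) match study weeks, which favours the first reading. Section 6, however, counts extension follow-up from the second transplant (weeks 4, 8 and 16), so the text does not settle it.

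**Step 3: literal non-responder scoring.** This assumes that the rule applies, that 9OL is ignored, and that 11 patients enter the extension (the figure assumed in Section 20, Microbiome Analyses). The result is 0/11. The exact upper 95% limit is 1 − 0.025^(1/11) = 28.5%. With 5 patients it would be 52%, and with 20 patients 17%.

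**Step 4: the endpoint at 9OL.** With assumed counts, exact 95% intervals are:
- 3/11 = 27% (6 to 61%)
- 6/11 = 55% (23 to 83%)
- 8/11 = 73% (39 to 94%)

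The estimate is imprecise but obtainable.

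**Step 5: effect on power.** The only power statement concerns remission in the randomised phase: 10 per arm, 10% against 77.5%. A two-sided Fisher exact calculation gives 80.2%, which agrees with the stated 80%. Nothing in it depends on this endpoint.

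**The case against.** The strongest reply is that this is a wrong week label and no more. Exactly one pouchoscopy is scheduled after open-label treatment, the overview, visit list and chart agree on it, and a sensible analyst would use it. That is right about the data: the score will exist under the current schedule.

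A reader might go further and infer that the endpoint can never be measured and that every extension patient would be scored a failure, 0 of 11. The documents do not support this, for four reasons.
- The non-responder rule operates within the intention-to-treat analysis. Section 1 assigns that analysis to remission and response, and in Section 20 the rule follows a list of primary and secondary endpoints. Neither place names this exploratory endpoint.
- The 0/11 result also requires the 9OL score to be disregarded.
- Eleven is a working assumption for counting stool samples, not a defined analysis set.
- Some endoscopic scores could fall near week 8 by chance. Section 16 asks for an endoscopy at premature withdrawal where possible. Also, the chart days are nominal: a patient with an early flare whose second transplant fell on day 28 would reach 9OL at day 28 + 28 = 56, eight weeks after the first transplant.

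What remains is that the stated time point matches no scheduled endoscopy, in all three places where the endpoint is defined. The accidental exceptions are a further reason to anchor the endpoint to a named visit.

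**Conclusion.** The endpoint is wrong as written: on either reading of week 8, the schedule provides no endoscopic subscore. This rests on the visit list, overview and chart, which agree with one another, and needs no outside assumption. It concerns every patient who enters the extension.

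The 0% result (0/11, 95% CI 0 to 28.5%) is a worst case that depends on a literal and doubtful extension of the non-responder rule, so it should be read as a risk and not as the expected outcome. The damage is limited to one exploratory, descriptive estimate in an uncontrolled extension. The primary endpoint, the secondary endpoints and the power statement are unaffected. The correction is worth making because the error is certain and the cost is small.

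**What to change.** 1. In the exploratory lists of Sections 1, 5 and 20, define open-label endoscopic improvement at the visit 9OL pouchoscopy (study week 10, extension week 4). This matches the timing of the first open-label remission and response endpoints.
2. State whether the baseline endoscopic subscore for the 2-point fall is the week 0 or the visit 6OL pouchoscopy.
3. In Section 20, state whether the non-responder rule applies to open-label endpoints and, if so, with what denominator.
4. Reconcile the Section 11 heading with Section 10 and the Section 21 charts. It omits 9OL, and it names screening where the chart has visit 1.

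The cost is a few wording changes. No procedure, visit or sample size changes. They should be made before any open-label endoscopic data are reviewed.

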	The outcome will be determined by the modified pouchitis disease activity index (mPDAI) and the need for antibiotic therapy to control symptoms. The mPDAI is a composite index consisting of 2 disease variables (clinical criteria of pouchitis: number of bowel movements, blood in stool, urgency and fever with a maximum score of 6 and endoscopy criteria of pouch inflammation with a maximum score of 6. The maximum combined score is 12).	
	 Complete remission is defined as a mPDAI score = 0 and no need for antibiotics. Clinical remission is defined as a clinical mPDAI score ≤ 4 and no need for antibiotics. Symptomatic improvement is defined as a decrease from baseline in the mPDAI clinical subscore of 2 points and no need for antibiotics. Symptomatic worsening of the disease is defined by an increase in the mPDAI clinical subscore of 2 points or the need for antibiotics. 	
	The severity of the pouch inflammation will be evaluated by two pouchoscopies (week 0 and week 4). Endoscopic improvement is defined as a decrease from baseline in the mPDAI endoscopic subscore of 2 points.	
Primary variables	Safety and tolerability of endoscopically and orally applied FMT	
Secondary variables:	 Clinical remission (mPDAI score ≤4 points) and no need for antibiotic therapy at week 4. Clinical remission (clinical mPDAI score ≤ 4) and no need for antibiotics at week 8*. Clinical remission (clinical mPDAI score ≤ 4) and no need for antibiotics at week 16*. Endoscopic improvement of active pouchitis (decrease from baseline in mPDAI endoscopic subscore ≥ 2 points) at week 4. 	

	 Response: Symptomatic improvement of active pouchitis (decrease from baseline in mPDAI clinical subscore ≥ 2 points) and no need for antibiotic therapy at week 4. Response: Symptomatic improvement of active pouchitis (decrease from baseline in mPDAI clinical subscore ≥ 2 points) and no need for antibiotic therapy at week 8*. Response: Symptomatic improvement of active pouchitis (decrease from baseline in mPDAI clinical subscore ≥ 2 points) and no need for antibiotic therapy at week 8*. Response: Symptomatic improvement of active pouchitis (decrease from baseline in mPDAI clinical subscore ≥ 2 points) and no need for antibiotic therapy at week 16*. 	
	*Only patients who do not continue in open label extension	
	• Exploratory analyses (OL=Open label):	
	 Endoscopic improvement of active pouchitis (decrease from baseline in mPDAI endoscopic subscore ≥ 2 points) at in open label extension week 8. 	

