	 Clinical remission (mPDAI score ≤4 points and a decrease in the baseline mPDAI> 2 points) and no need for antibiotic therapy at week 10 OL. 	
	 Clinical remission (clinical mPDAI score ≤ 4) and no need for antibiotics at week 14 OL. 	
	 Clinical remission (clinical mPDAI score ≤ 4) and no need for antibiotics at week 22 OL. 	
	• Response: Symptomatic improvement of active pouchitis (decrease from baseline in mPDAI clinical subscore ≥ 2 points) and no need for antibiotic therapy at week 10 OL.	
	 Response: Symptomatic improvement of active pouchitis (decrease from baseline in mPDAI clinical subscore ≥ 2 points) and no need for antibiotic therapy at week 14 OL. 	
	 Response: Symptomatic improvement of active pouchitis (decrease from baseline in mPDAI clinical subscore ≥ 2 points) and no need for antibiotic therapy at week 22 OL. 	
	 Symptomatic worsening of active pouchitis (decrease from baseline in mPDAI clinical subscore ≥ 2 points) from FMT week 0 – week 16 Quantitative changes in mPDAI from baseline values 	
	 Quantitative changes of calprotectin from baseline 	
	Alterations in stool microbiome after FMT	
	Engraftment of donor FMT	
Statistical analysis:	Remission and response as defined by mPDAI scores will be analysed by intention-to-treat design. Wilcoxon rank sum tests will be carried out to assess differences in the pre- and post-treatment mPDAI total scores and subscores. P values < 0.05 will be considered to be statistically significant.	
Duration of study	2 weeks of FMT/ placebo therapy followed by evaluation of clinical and endoscopic outcome at week 4, and clinical evaluation at week 8 and 16. In case the study patients does not achieve clinical remission at week 4 or	

	experiences a flare of disease on day 15-28 after start of the study he/she will be offered the possibility to participate in open label extension with an additional endoscopic FMT followed by 2 weeks of oral FMT and clinical follow up at week 10, 14 and 22.
	The anticipated time of the overall study is 18 months
Number of centres:	Single center study

2. BACKGROUND:

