At phone visit 4 the coordinator will ask the study patient if adverse events occurred and review the adverse event diary. The coordinator will evaluate the clinical components of the mPDAI of the last 3 days before the phone call (stool frequency, rectal bleeding, fecal urgency/ abdominal cramping, fever) as well as the concomitant medications. If the patient is in remission according to the diary (mPDAI \leq 4) and is on no concomitant medications, a pouchoscopy will be planned for site visit 5. If the study patient is not in remission (mPDAI \geq 4) or had an early relapse after FMT the open label extension will be offered and the patient can be started on oral antibiotics again. For safety analyses a site visit 5 should be planned in the following 3-4 days. If the study patient chooses not to participate, he should be followed according the same schedule as patients who are in remission.

Early termination visit due to flare on day 1-28 after FMT or due to adverse event or patient unwillingness to continue in study necessitating early termination

If at any time between day 1-28 after endoscopic FMT the patient experiences recurrence of his pouchitis symptoms, he/she will contact the coordinator. The coordinator will ask the study patient if adverse events occurred and review the adverse event diary. The coordinator will evaluate the clinical components of the mPDAI of the last 3 days before the phone call (stool frequency, rectal bleeding, fecal urgency/ abdominal cramping, fever) as well as the concomitant medications.

If the study patient has active disease (mPDAI>4), an early termination study visit will be scheduled. A physical exam will be completed and, if possible, stool will be collected before the start of antibiotic therapy as standard of care. Blood labs will also be collected. The patient will be started on the same antibiotic, which he was on before entering the study. At the study visit the coordinator will review possible adverse events, evaluate the clinical components of the mPDAI of the last 3 days before the visit (stool frequency, rectal bleeding, fecal urgency/ abdominal cramping, fever) as well as the concomitant medications. If the patient wants to proceed into the open label study, he has to undergo at least 10 days of standard of care antibiotic therapy, before he can undergo the open label therapy with FMT (endoscopic and oral FMT).

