Dispense oral FMT or placebo Dispense omeprazole 20 mg (1 tablet) daily for 14 days during oral FMT Dispense PDAI diary Dispense adverse events diary

Pouchoscopy: Evaluation of endoscopic PDAI and perform "blinded" (real or placebo) FMT.

• Visit 2: Phone visit week 1 (7 (+1 day) days after endoscopic FMT /placebo and on oral FMT/placebo)

Formal aspects:

Adverse events (review adverse events diary)

Concomitant medication

Calculation of clinical mPDAI (stool frequency, rectal bleeding, fecal urgency/abdominal cramping, fever)

• Visit 3: Site visit week 2 (15 +3 days after endoscopic FMT /placebo and on oral FMT/placebo)

Formal aspects:

Adverse events (review adverse events diary)

Concomitant medication

Calculation of clinical mPDAI (stool frequency, rectal bleeding, fecal urgency/abdominal cramping, fever)

Reminder stool collection on day 15, 16 or 17 (day 1-3 after end of oral FMT) and bring in stool.

• Visit 4: Phone visit week 4 (2-3 days before planned week 4 site visit)

Formal aspects:

Adverse events (review adverse events diary)

Concomitant medication

Reminder to bring stool day 25, 26 or 27.

Calculation of clinical mPDAI (stool frequency, rectal bleeding, fecal urgency/abdominal cramping, fever)

If patient is in clinical remission (mPDAI ≤ 4) and no need for antibiotics plan for pouchoscopy week 4

If patient is not in clinical remission (mPDAI > 4) or need for antibiotics or comes in due to exacerbation of symptoms with possibility to continue with open label extension. Need to restart 10 day course of antibiotics as standard of care similar to initial antibiotic treatment before the first FMT

• Visit 5: Site visit Week 4 (day 28 +/- 3 days after first transplant) or early termination visit due to flare (day 1-28 after first transplant)

Examinations

Vital signs: blood pressure (mm Hg), heart rate (min-1), weight (kg), temperature

Physical examination:

- Head (including ENT and eyes)
 Lymphatic system
 Endocrine system
 Lungs and respiratory tract
 Peripheral vascular system
 Skin and connective tissue
- Cardiovascular system

- Other

each: actual status: Present finding / normal condition / not examined

Measurement of laboratory parameters

Hematology Serum chemistry

Stool collection: Bring to visit.

Formal aspects:

Return of study medication (empty containers)

Compliance assessment (count of empty containers returned)

Concomitant medication

Adverse events (review adverse events diary)

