22. APPENDIX B: STUDY FLOW CHART

23. APPENDIX C: MODIFIED POUCHITIS DISEASE ACTIVITY INDEX (MPDAI)

According to Shen et al.; 2003 67

Clinical Criteria	Score
Stool Frequency	
Usual post-op stool frequency	0
1-2 stools/day > post-op usual	1
3 or more stools/day > post-op usual	2
Rectal Bleeding	
None or rare	0
Present daily	1
Fecal Urgency / Abdominal Cramps	
None	0
Occasional	1
Usual	2
Fever (temperature> 100°F)	
Absent	0
Present	1

Endoscopic Criteria

Edema	1
Granularity	1
Friability	1
Loss of vascular pattern	1
Mucus exudate	1
Ulceration	1

24. STUDY PATIENT STOOL DIARY

:				
ing in your diary each night. You	should record before going to be	ed and the answers should describ	be the preced	ing 24 hours.
During the past 24 hours how many bowel movements did you have? (Please provide number)	During the past 24 hours how many of your bowel movements contained blood? (Please provide number)	During the past 24 hours how many of your bowel movements were preceeded by abdominal cramps or an urgent need to go to the bathroom? (Please provide number)	you experi than 37.8°	past 24 hours did ence fever higher C (100.0°F)? rk "yes" or "No")
			Yes	No
	During the past 24 hours how many bowel movements did you have?	During the past 24 hours how many bowel movements did you have?During the past 24 hours how many of your bowel movements contained blood?	During the past 24 hours how many bowel movements did you have?During the past 24 hours how many of your bowel movements contained blood?During the past 24 hours how many of your bowel movements contained blood?(Please provide number)(Please provide number)During the past 24 hours how many of your bowel movements contained blood?	many bowel movements did you have? (Please provide number)many of your bowel movements contained blood? (Please provide number)many of your bowel movements were preceeded by abdominal cramps or an urgent need to go to the bathroom? (Please provide number)you experie than 37.8°G (Please materia)Image: Strength of the strengt of the strength of the strength

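### The exploratory endpoint of symptomatic worsening is defined in the wrong direction in all three endpoint lists, and the lists leave out the antibiotic component of the protocol's own definition

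*Combined protocol and SAP*

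**What the plan says.** The endpoint appears three times with the same rule: among the exploratory analyses in the Protocol Summary (Section 1), in Section 5 (Trial Endpoints) and in Section 20 (Statistical Analysis). Section 20 reads "Symptomatic worsening of active pouchitis (decrease from baseline in mPDAI clinical subscore ≥ 2 points", and the period runs from week 0 to week 16. None of the three entries mentions antibiotics.

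The same lists define Response with the same score rule plus an antibiotic condition: "Response: Symptomatic improvement of active pouchitis (decrease from baseline in mPDAI clinical subscore ≥ 2 points) and no need for antibiotic therapy at week 4".

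The Criteria for Evaluation row of the Protocol Summary says the opposite about worsening: "Symptomatic worsening of the disease is defined by an increase in the mPDAI clinical subscore of 2 points or the need for antibiotics". The same row ties antibiotic need in the outcome assessment to the control of symptoms.

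Appendix C fixes the direction of the scale. Usual postoperative stool frequency scores 0, and "3 or more stools/day > post-op usual" scores 2. Bleeding, urgency or cramps, and fever also score more points as they get worse.

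**The concern.** Two entries in one list carry the same score criterion under opposite labels. Since a higher clinical subscore means more symptoms, a fall cannot be worsening. Section 20 is the text an analyst would program from, and its Clinical analyses paragraph promises a percentage with a 95% confidence interval for each dichotomous outcome. Followed literally, the reported worsening rate would be made up of patients whose symptoms improved.

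The missing antibiotic component is a separate fault. If only the direction is corrected, a patient whose score stays level because antibiotics were restarted is not counted under the lists, but is counted under the Protocol Summary definition.

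**Working it through.** **Inputs.** The clinical subscore runs from 0 to 6 (Criteria for Evaluation). Appendix C agrees: stool frequency 2 + bleeding 1 + urgency or cramps 2 + fever 1 = 6. Let B be the baseline subscore, F the follow-up subscore, and A = 1 if antibiotics are needed, otherwise 0. The Protocol Summary says 2 points where the lists say at least 2; I read both as at least 2.

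- Response (all three lists): F − B ≤ −2 and A = 0.
- Worsening as listed (Sections 1, 5 and 20): F − B ≤ −2, whatever A is.
- Worsening as defined (Criteria for Evaluation): F − B ≥ 2 or A = 1.

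**Step 1: the plan's only power figure.** Section 20 states 80% power for remission of 10% against 77.5%, with 20 patients randomised 1:1 and a two-sided Fisher exact test at 0.05. Power is the sum of the products of the two binomial probabilities (10 patients per arm) over all tables with p ≤ 0.05. The result is 0.802, which reproduces the stated 80%. The worsening endpoint does not enter this calculation.

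**Step 2: direction, by example without antibiotics.** A change from 5 to 3 is worsened under the listed rule and not worsened under the definition. A change from 1 to 3 is the reverse. A patient with a baseline of 0 or 1 cannot fall by 2 points, so the listed rule can never count that patient, whatever happens later.

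**Step 3: all combinations.** There are 7 × 7 score pairs and two antibiotic states: 7 × 7 × 2 = 98 combinations.

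- Pairs with a fall of at least 2: 5 + 4 + 3 + 2 + 1 = 15. By symmetry, 15 pairs have a rise of at least 2.
- Response: 15 pairs with A = 0, so 15 combinations.
- Worsening as listed: 15 × 2 = 30.
- Worsening as defined: 49 with A = 1, plus 15 with A = 0 and a rise, so 64.

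| Rule | Combinations counted (of 98) | Response combinations counted as worsening (of 15) | Defined worsening missed (of 64) |
|---|---|---|---|
| As listed | 30 | 15 | 64 − 15 = 49 |
| Direction corrected only | 30 | 0 | 64 − 30 = 34 |
| Protocol Summary definition | 64 | 0 | 0 |

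The 15 combinations that the listed rule shares with the definition are those in which the score fell but antibiotics were needed. The listed rule reaches them because of the fall, not because of the antibiotics. The counts are unweighted and show how the rules behave; they do not predict how many patients fall in each group.

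**The case against.** The strongest reply is that this is a copying error with one sensible reading. The label says worsening, the scale runs upward, and the Protocol Summary has the only sentence framed as a definition. A careful analyst would notice. The list also includes quantitative change in mPDAI, which would show deterioration in any case. Much of this stands: the intended direction is not in doubt, and the scope is one exploratory endpoint in a 20-patient proof-of-concept trial. It does not remove the point. The error is repeated in three lists, including the one that governs the analysis. Recognising it also leaves the antibiotic component and the threshold unsettled, and those choices would then be made after data are available.

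A reader might infer more from the open-label extension. A patient who flares and wants to enter is told that "he has to undergo at least 10 days of standard of care antibiotic therapy, before he can undergo the open label therapy with FMT". It is tempting to conclude that copying in the antibiotic component would class responders as worsened merely for this course. The documents do not establish that. At visit 5 the mPDAI is calculated before pouchoscopy, and footnote h of the visit charts allows open-label FMT only without remission at visit 4, a phone visit where only the clinical subscore exists. Entry by score above 4 then needs a 5 or 6, and a fall of 2 to reach 5 would need a baseline of 7 on a scale that ends at 6. Entry through antibiotic need fails Response by definition. The open-label chart title does mention patients with response only, and Section 7 has one passage with a cut-off of 4 or more, so the texts are not fully aligned, but they do not support the inference. The Protocol Summary also links antibiotic need to controlling symptoms, which argues against counting a preparatory course automatically.

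A reader might also infer that worsening to week 16 cannot be assessed in open-label patients, or that this endpoint lacks a restriction it should carry. For an endpoint covering a period, five open-label visits are scheduled between the second FMT and week 16, and Section 7 has the stool diary kept daily until visit 12OL. The restriction "Only patients who do not continue in open label extension" is a footnote to the secondary list; no exploratory entry carries it, so its absence here shows nothing.

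**Conclusion.** The point holds. Symptomatic worsening is reversed in all three endpoint lists, repeats the Response score criterion, and omits the antibiotic component of the protocol's own definition. Applied as written, every patient meeting Response at an assessment is also counted as worsened at that assessment, and a rise of at least 2 points never counts.

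The conclusion on direction rests only on the texts and on the scale in Appendix C. The combination counts also assume that 2 points means at least 2. The consequence is confined to this exploratory endpoint. The primary safety endpoint, the secondary endpoints and the power statement are unaffected. It should be corrected because the error is certain and the correction nearly free, not because it threatens the trial's main conclusions.

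**What to change.** 1. In the exploratory lists of the Protocol Summary, Section 5 and Section 20, change *decrease* to *increase* in the worsening entry, keeping the threshold of at least 2 points on the clinical subscore.
2. Reconcile the three lists with Criteria for Evaluation on whether need for antibiotics is part of the endpoint.
3. Align 2 points with at least 2 points. Criteria for Evaluation uses the bare figure for symptomatic improvement and endoscopic improvement too, so change all of them together.
4. In Section 20, state for the analysis of this endpoint whether the antibiotic course taken before open-label FMT counts as need for antibiotics, given the Protocol Summary's reference to controlling symptoms, and whether time in the open-label extension is included in the week 0 to week 16 period.

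The cost is one word in three places, the wording changes in items 2 and 3, and one or two analysis sentences. No new data, visits or changes to patient care are needed. The changes should be made before outcome data are examined.
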